Covariates. Parent covariates (race/ethnicity, gender, family income, duration of caregiver role) will be recorded on the enrollment form. Child covariates. Functional status will be measured using the 14-item Functional Status II-Revised (FS II-R);¹²⁵ higher scores indicate higher function. The type of technology used by the child will be recorded on the PI-developed Technology Dependency Questionnaire and analyzed using dummy codes for regression.

Intervention Exit Survey. This survey will be delivered to eligible intervention arm participants to assist with future intervention delivery improvements.

Descriptives. The parent's characteristics (age, marital status, education) will be recorded using the enrollment form. The amount of outside lay caregiving assistance and home nursing will be recorded on the Information and Support Form. Interpersonal support will be measured by the 12-item Interpersonal Support Evaluation List (ISEL).^{126,127} Higher scores indicate greater social support. The technology-dependent child sample characteristics (age, gender, primary medical diagnosis) will be recorded on the enrollment form.

Design and methods to achieve robust and unbiased results (Rigor). This carefully powered 9-month RCT is designed to achieve robust results incorporating safeguards to reduce error. First, we have selected psychological measures with excellent psychometric properties. Measures to assess biological processes (sleep, cortisol) were chosen for their ability to directly measure the process or marker being studied—a gap identified in prior research—thus reducing another source of error. Second, we have developed our analytic plan to incorporate relevant covariates and will achieve unbiased results by including an additional statistician to evaluate reproducibility of results via a confirmatory analysis of study findings. By comparing analytic results from two statisticians, we will establish reproducibility of results and ensure the robustness of our findings.

Study results will be generalizable to parent caregivers of technology-dependent children with complex chronic conditions. We have broad inclusion criteria, increasing generalizability of results. All parent caregivers' children will be technology-dependent with a range of complex, chronic conditions. Based on prior work, we expect our sample to range in age from 18-65 years and represent all income levels. Some parent caregivers may be up to 80 years old. We will also have representation of male caregivers, often underrepresented in such research.

Data Management. We will use numbers rather than names to identify parents on all study forms to maintain confidentiality. Identifying data and consent forms will be separated from the study data and kept in a separate, locked file cabinet. Data will be entered into password-secured, encrypted computer files. Each subject will have a separate file stored in a locked cabinet. The data will be stored on a server folder accessible to only the PI, research staff, and Information Technology department staff. A Study Operations Manual will include procedures for subject recruitment, data collection and coding, and data management. The Graduate

Student Research Assistant will be responsible for the day-to-day data management of the study.

Estimated time required (minutes)	Pre-Screening	Time 1	Time 2	Time 3	Time 4	Time 5
	1 minute					
Data Collection	N/A	60	45	45	45	45
Weekly calls x first 4 weeks (control group)		2-4	2-4	2-4	2-4	
Weekly calls x first 4 weeks (intervention group)		5	5	5	5	
RTI session with Interventionist after random assignment		60				
RTI booster sessions at 2 months & 4 months post intervention		10	10			
RTI booster follow up call 1 week after booster session at 2 months & 4 months post intervention		2-3	2-3			

Aims 1 & 3: Analysis of the monthly rate of change for each parent outcome in each arm will be estimated via linear mixed models and fit using SAS PROC MIXED.^{128,129} Each model will include a random intercept and slope (possibly modeled using a polynomial spline) to account for between-subject variance in each outcome over time. Conditional on these random effects, we will explore within-subject variance in each outcome over time using different residual covariance structures and select the most appropriate structure using likelihood-based criteria. Fixed effects will include a continuous variable to represent time since randomization, an indicator variable to represent the intervention, and stratification factors used during randomization (facility, OTA technology group, race/ethnicity). Assuming a linear rate of change over time, the regression coefficient of the terms representing interactions between time and the intervention indicator variable will be used to estimate the difference in the monthly rate of change in each outcome between arms.

Aim 2 & 4: To determine if resourcefulness mediates the effect of the RTI[©] on parent outcomes (psychological and physical health, self-management behaviors), a theory-based causal mediation model^{130,131} will be fit using separate linear mixed models of parent outcomes at 3 months after randomization that adjust for the intervention indicator variable, stratification factors, and the mediator at 6 weeks after randomization. This model will allow us to decompose the total effect of the RTI on parental outcomes at 3 months into direct and indirect (or mediated) effects and estimate the proportion of the total effect that is mediated. Variance estimates and 95% confidence intervals will be estimated using a bootstrapping procedure based on 1000 bootstrap samples. To more fully explore the temporal pattern of mediated effects, we will use similar models to estimate the mediated effect using measurements of the mediator and parental outcome taken at other time points as well (e.g., total effect of RTI[©] on parent outcomes at 6 months that are mediated by personal and/or social resourcefulness at 3 months).

Aim 5: To assess the relationship between self-management behavior and parent psychological and physical health outcomes, we will use correlational and regression analyses. The effect of RTI[©] on outcomes will be estimated after controlling for important covariates in the structural equation model (SEM). Also, we will study parental psychological and physical health outcomes and its association with sleep (or positive health practices), using the SEM framework. The SEM is a general, flexible, powerful, and comprehensive methodology for representing, estimating, and testing a network of relationships among variables of interest. By the use of SEM, we will be able to develop a hypothetical model or path diagram that allows for specification of relationships and the directionality of the relationships among the variables of interest. These exploratory models or path diagrams that are derived from this study will be a basis for further study/validation. In the model fitting, we will use the method of maximum likelihood estimation (MLE) for estimating parameters.

To account for any multiple comparisons, a Bonferroni-corrected, two-sided significance level will be applied to all analyses for all aims. Additionally, we expect some level of missing data at each time point. To adjust for the missing data in all mixed-models analyses, we will apply pattern-mixture models to each model to ensure that missing data is adequately accounted for in each analysis. In contrast to a “completers only” approach, pattern-mixture models will provide a consistent and asymptotically efficient estimate of the effect of intervention on the monthly rate of change in parent outcomes when data is missing not at random.

Aim 6: We will analyze the technology-dependent children's ER visits, hospital days over 9 months using a Poisson regression model that adjusts for the intervention indicator variable and important covariates. This model will allow us to compare the relative rate of ER visits, hospital days between the two arms.

Secondary Analyses. To obtain more precise estimates of the intervention effect on the time point interval rate of change in each parent outcome, additional multivariable analyses will characterize and estimate the relationship between potential covariates at baseline and each outcome. For continuous variables lacking a linear relationship with the outcome, appropriate transformations or categorization will be considered. For nominal and ordinal variables, the number and type of categories will be considered to obtain the optimum relationship, if any, with the outcome. Based on a two-sided significance level of 0.15, any baseline covariate found to be associated with the outcome will be included in the model described for the Primary Analyses.

Modification of the intervention effect on the monthly rate of change in each parent health outcome will also be tested in each model by including an interaction between a prespecified effect modifier measured at baseline, the intervention indicator variables, and the variable representing time since randomization. Should an interaction be detected based on a two-sided significance level of 0.05, the monthly rate of change in each outcome will be estimated in each of the arms for each level of a categorical effect modifier or at the 25th, 50th, and 75th percentiles of a modifier that is measured on an interval scale. A similar analysis will be conducted to examine possible effect modification of the intervention effect on positive health practices, by including an interaction between the intervention indicator variables and the prespecified effect modifier.

Sensitivity analyses will also be applied to all mediation models described for the Primary Analysis to evaluate the assumption of sequential ignorability (no unmeasured confounders of the association between the mediator and each parent outcome). As described by Imai et al.,¹³¹ this analysis assesses how large an effect an unobserved confounder must have on both models to cause a nonsignificant mediated effect.

There are few risks to participants. A potential emotional risk during the interview is that recalling information regarding their child's course of illness and home management difficulties may make some parents uncomfortable. The interviewer will be vigilant to assess the parent's discomfort. Parents experiencing considerable discomfort will be asked if they wish to stop the interview and will be given supportive assistance by the interviewer. The parent will then be told to contact their primary care provider and given a resource sheet with the number of United Way First Call (211) to access on-call mental health professional services in their local area or Cuyahoga County 24-Hour Mental Health Crisis Information and Referral [contact]). If any participant is noted to have a level of depressive symptoms above the recognized clinical *T* score of 55.1 (raw score \geq 16- mild depressive symptoms) on the Patient-Reported Outcomes Measurement Information System (PROMIS) Short Form v 1.0-Depression 8a measure, he/she will be told of the findings and given instructions to contact his/her primary health care provider and the resource sheet with mental health contact phone numbers as above (See Mental Health Resources Decision Tree). Any parent expressing signs or symptoms of major depression (i. e., hopelessness and/or helplessness) in the enrollment interview, Resourcefulness Training appointment, telephone follow-up, journal writing, data collection appointments, booster sessions, or parents with a PROMIS-Depression 8a score of \geq 22 (moderate to severe depressive symptoms) or a Depressive Cognitions Scale score of \geq 7, will be assessed for imminent risk of suicide by asking if they have had any thoughts of harming

themselves in any way or perhaps killing themselves. If the answer to any portion of the question is "yes" the participant will be told of a concern for their safety and the necessity for the interviewer to contact the Crisis Team from the Cuyahoga County 24-Hour Mental Health Crisis, Information and Referral Hotline immediately. The consent form will specifically discuss this risk. The research team members will notify the PI of any need to activate the above plans for the Crisis Team or referral to the 24-Hour Mental Health Crisis Information and Referral Hotline. Throughout the study, all research team members in contact with subjects will also assess for other psychiatric symptoms that might require intervention from the Crisis Team or the above 24-Hour Mental Health Hotline. Co-Investigators [name] and [name] are psychiatric nurses and can provide consultation to the Interventionist and data collectors when needed. Also, physical risks might involve fatigue due to the length of time (about 45 -50 minutes) needed to answer the study questions and about 1 hour for the Resourcefulness Training[®] intervention and practice journal entry. There is a slight inconvenience for all participants will need to take scheduled phone calls as per protocol, schedule time to meet with data collectors, wear Actiwatch at specified times and mail them back to study office. The intervention group will experience slight inconvenience due to time for intervention session, time to write in semi-structured journal 2-3 minutes daily for 4 weeks and 1 week booster journals (2 months, 4 months post intervention). Finally, there is a minimal risk to loss of confidentiality with collection of data particularly with the collection of Personal Health Information regarding the technology-dependent child. The consent form will specifically discuss these risks.

There is a slight risk of developing skin irritation from the Actiwatch. The participant will be instructed at enrollment that if any redness of the skin develops in the area where the watch is worn they are to remove it and contact the study office. There is also a very rare risk during hair sample collection of a minor scalp laceration (a cut) and infection related to same.

All participants are volunteers and non-participation and withdrawal from the study are alternatives to study participation. Parents will be told that they may withdraw from the study at any time. There are no risks to non-participation or withdrawal from the study. The Project Director (at recruitment) and the data collectors (at enrollment) will explain that participation or non-participation will have no effect on the type, quality, or nature of medical care that the technology-dependent child receives, and that all research data will be obtained by an Interventionist or data collector and will not be communicated to any healthcare personnel at the healthcare facility.

Writing about the stress of caring for their child in their journal might bring out uncomfortable feelings. Parents will be instructed that if they experience distress, they may stop the journaling and contact the research staff. In addition, they will be instructed to tell the research staff about these feelings during the weekly follow-up telephone calls. If needed, we will provide emotional support and refer them to mental health resources such as the 24-Hour Mental Health Crisis, Information and Referral Hotline as detailed in the above description of risks. We have past experience teaching journal writing, analyzing journal entries, and reviewing entries for psychological distress. To minimize potential problems, we will collect journals after 1 month. Drs. [name] and [name], psychiatric-mental health nurses, will oversee online log writing analysis for high-risk mental health situations, and follow up as needed. In past experience with journal writing, no psychological distress has occurred. Additionally, we will make weekly follow-up phone calls for the first 4 weeks of the intervention to monitor for signs of psychological distress.

To reduce the risk of a breach in confidentiality we will assign each subject a code number and not include names on any study materials. UH REDCap will be used for any prescreening, data collection and any follow up information. In any sort of report we might publish, we will not include any information that will make it possible to identify subjects. Any hard copy lists will be kept in a locked file and access will be limited to the researchers, the review board responsible for protecting human subjects, regulatory agencies, and sponsors and funding agencies. Voice recorders will be stored in a locked file cabinet following data collection. The list linking the participant name, contact information and study ID will be destroyed 5 years after completion of the study. Participants will also be told that individual responses will not be shared with others. Participant names will not be used in any reports of the study.

All information obtained during data collection will be kept confidential and will be disclosed only with the participant's permission or as required by United States or Ohio law such as abuse of their children. If disclosure is made by the participant regarding harm of themselves or others, the appropriate agencies such as the 24 Hour Mobile Crisis Team or the Ohio Department of Job and Family Services ([name]) will be notified as per study adverse event/ serious adverse event, abuse protocol. If a participant discloses domestic abuse/violence to a member of the study team the study adverse event, serious adverse event, abuse protocol will be implemented that includes giving the phone number to the Domestic Violence [contact]-SAFE.

To maintain participant privacy, all interviews will be conducted in a private area in a place of the mother's/father's choosing such as her/his home, public library, place of employment, private place in a coffee shop or the Dahms Clinical Research Center. Privacy will be maintained as well in the procedures for identifying participants as described above. Participants will be mailed an introductory letter prior to study staff making telephone contact. We will respect their wishes related to the best way to maintain contact with them (phone, text, email).

Facebook and Twitter will be used to post the IRB flyer about the study. A "Friend" request will be sent to parent caregiver organizations who have members likely to meet inclusion criteria along with an introductory letter about our study and the request to post our recruitment flyer. The organization can make a decision to accept or reject the request to post our study flyer. Potential participants reached through either Facebook or Twitter would then self-identify and voluntarily contact us to hear more about the study and decide on participation. When they contact the study staff they will be screened for eligibility including residence within Northeast Ohio for face-to-face data collection.

Participants may receive some benefit from the stress reducing methods used in this study (Resourcefulness Training, writing in log). The potential risk for emotional distress is minimal and reasonable given the potential benefit for reducing stress and improving a parent's psychological and physical health outcomes and self-management behaviors (sleep, positive health practices). This study will benefit other families by aiding in our understanding of what methods help parents reduce stress and promote optimal psychological and physical outcomes and self-management behaviors when they are caring for a technology-dependent child. It is hoped that parents who participate in the

Resourcefulness Training arm of the study will feel more confident as they implement resourcefulness skills over the intervention period and will have a reduction in negative impact of caregiving over time. In addition, it is believed that the Resourcefulness Training intervention will enhance the care delivery by the parents and decrease the number of emergency room visits and hospitalizations.

Possible causes for the participant to be withdrawn from the study include that the child with special medical technology has become too ill or has died. The participant may decide to withdraw from the study due to lack of interest to complete the remaining questionnaires at T2, T3, T4, T5 or that she/he is not interested in continuing to complete the journal writing. If the participant indicates an intent to withdraw from the study, she/he will be invited to share reasons for desire to withdraw from study. Participants will not be followed after they have voluntarily withdrawn from the study unless they indicate that they wish to be contacted in the future for any follow-up studies. If the child has the special medical technology removed during the course of their parent's participation in the study we will continue to conduct data collection but will note removal of technology in analysis.

There is no reimbursement for parking and meals but an incentive will be given to participants for their time and inconvenience. Participants will be given a \$25 gift card at each of 5 time points following completion and return of the questionnaires. The total payment will be \$125 over the study time if they complete all portions (5 data collection points) of the study. They will also receive a \$5 gift card each of the 4 time points they need to return the Actiwatch and sleep history booklet to the study office. The total payment for returning these items each time (4 time points) is \$20.

Data and safety monitoring will be conducted to determine if data collection should be altered or stopped. Every 6 months the DSM Committee will assess the risks and benefits of the study by reviewing individual adverse events and unanticipated problems that have occurred during the study. Data monitoring will include a review of the accuracy, validity, reliability and completeness of data collection. [name], the principal investigator will make the decision related to altering the study in collaboration with the committee if more than two mothers/fathers experience significant discomfort or distress that required a referral to United Way First Call.

Data and safety monitoring will be conducted to determine if data collection should be altered or stopped. Every 6 months the DSM Committee will assess the risks and benefits of the study by reviewing individual adverse events and unanticipated problems that have occurred during the study. The committee members are not part of the research team. This committee will review data on this study regarding 1) study safety, including auditing selected cases for compliance with IRB requirements, conformance with informed consent requirements, verification of source documents, and investigator compliance; 2) minimizing research-associated risk; and 3) protecting the confidentiality of participant data. In addition, it will review (1) all causes of mortality and (2) issues with participation. The rate of recruitment refusal (percent and reasons) and subject

attrition (percent and reasons) will be tracked and reported at these reviews. Differential attrition from the intervention and control arms also will be monitored. Written reports will be developed and submitted to the committee by the CWRU PI, [name], the principal investigator will make the decision related to altering the study in collaboration with the committee if more than two mothers/fathers experience significant discomfort or distress that required a referral to United Way First Call. [name] will be responsible to submit written reports to any funding agency within 2 weeks of the meeting. If concerns or problems are identified by the SMC, they will be reported to the IRB and funding agency via email by [name] within 3 business days after they are identified. If there are recommendations made by the SMC, the action plan for response or notice of any actions taken by the IRB regarding the research and any responses to those actions will be provided to Funding Agency Officials within 2 weeks.

References

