Resourcefulness Intervention to Promote Self-Management in Parents of Technology-Dependent Children

NCT04105244

11/8/2022

The purpose of this randomized controlled trial is to test the effectiveness of a Resourcefulness Training Intervention (RTI[®]) designed for parent caregivers of technology-dependent children on the parents' (a) psychological and physical outcomes at 6 weeks, 3 months, 6, and 9 months post-intervention; and (b) self-management behaviors (sleep, positive health practices) over 9 months post-intervention. Theoretical underpinnings of the RTI posit that caregivers with greater resourcefulness will experience less stress and are better able to maintain self-management behaviors than caregivers with lower resourcefulness.^{28,30} Therefore, RTI[®] (©1995, [name]) is hypothesized to improve a parent's psychological and physical outcomes and self-management behaviors, enhancing his/her ability to deliver care to a technology-dependent child.^{15,18,29,47} We plan to measure the effects of RTI on resourcefulness, parent outcomes, and self-management behaviors (sleep, positive health practices).

The specific aims of the study are to: **Aim 1:** Determine whether the RTI versus Attention Control improves psychological (mental HRQoL, depressive cognitions, depressive symptoms, appraised stress, burden) and physical outcomes (physical HRQoL, chronic stress [hair cortisol]) over 9 months in parents of technology-dependent children, after controlling for covariates (parent race/ethnicity, gender, family income, caregiving duration, and children's functional status, technology type).³² **Aim 2:** Determine whether changes in psychological and physical outcomes are mediated by changes in parents' levels of resourcefulness based on intervention condition. **Aim 3:** Compare self-management behavior (sleep, positive health practices) over 9 months in parents who received RTI versus Attention Control. **Aim 4:** Explore whether resourcefulness is a mediator between intervention condition and self-management behaviors, controlling for baseline sleep and positive health practices over 9 months. **Aim 5:** Explore the relationship between self-management behavior and parent psychological and physical outcomes based on intervention condition. **Aim 6:** Compare target children's healthcare use (ER visits, hospital days) over 9 months based on parent intervention condition.

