The proposed study is a longitudinal (9-month) RCT in which primary caregiver parents (as defined in inclusion criteria) of technology-dependent children will be randomly assigned to one of two study arms: (1) The **Attention Control arm** will receive weekly phone calls for the first 4 weeks and at 2 and 4 months post-enrollment plus the current standard of care, whereby caregivers phone their healthcare providers when they have questions or concerns; and (2) The **Resourcefulness Training[©] arm** will receive (a) individually tailored instruction on personal and social resourcefulness skills via the Resourcefulness Video and interventionist, (b) instruction for the online log-writing (via REDCap) so for the parent to describe resourcefulness application, (c) access to the study website with videotape vignettes and Resourcefulness Video, and (d) boosters at 2 and 4 months post-enrollment that will include reinforcement of skills learned and additional online log writing. Measures of parents' outcomes (mental and physical HRQoL, depressive cognitions, depressive symptoms, appraised stress, and burden) and self-management behaviors (appraised/objective sleep, positive health practices) will be obtained at enrollment (T1), then 6 weeks (T2), 3 months (T3), 6 months (T4), and 9 months (T5) post-enrollment to analyze the immediate, extended, and long-term effects of the intervention on parents' outcomes. Chronic stress will be measured by obtaining parents' hair cortisol levels and objective sleep by actigraphy at T1, T3, T4, and T5 to examine changes over time. We will also obtain measures of the mediating (personal and social resourcefulness) variable and covariates (caregiver's race/ethnicity, gender, family income, duration of caregiving, child's functional status, and type of technology).

Research Procedures. The Project Director will notify the data collector of potential participants. He/she will schedule an appointment at a mutually agreed upon time and in a private place of the parent's choosing (e.g., parent's home, library). At that meeting, the data collector will have the parent read the consent form and answer any questions. After written, informed consent is obtained, the data collector will collect baseline (T1) data (questionnaires),

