1.2 Global Health Scale.^{108,109} The PROMIS[®] measures have been extensively tested and demonstrate excellent psychometric properties. Depressive cognitions will be measured by the 8-item Depressive Cognitions Scale¹¹⁰ to assess cognitive symptoms that precede depression;¹¹¹ higher scores indicating more depressive cognitions.^{110,112} Depressive symptoms will be measured by the 8-item PROMIS[®] Short Form v 1.0-Depression 8a.¹¹³ A clinically significant *T* score of 60 (raw score ≥ 22) requires action steps (see Human Subjects).¹¹⁴ Appraised stress (subjective) will be measured by the 10-item Perceived Stress Scale¹¹⁵ (NIH Toolkit); higher scores indicate greater stress. The level of chronic stress will be measured by a hair cortisol sample that measures cortisol level over the past 3 months.^{68,90,116} Caregiver burden will be measured using the Zarit Burden Interview-12, a 12-item tool assessing caregiver burden, with higher scores indicating higher burden.¹¹⁷ While originally developed for caregivers of older adults, it has been successfully used with parent caregivers.^{118,119}

Self-Management Behaviors: Appraised sleep quality will be measured by the Pittsburgh Sleep Quality Index (PSQI), a 19-item, self-report measure of sleep disturbance in adults.¹²⁰ It provides a global score that includes 7 subscale scores: sleep quality, sleep duration, sleep latency, sleep disturbance, habitual sleep efficiency, daytime dysfunction, and sleep medications over the past month. A global sum of ≥ 5 indicates a “poor” sleeper.¹²⁰ Objective sleep patterns (total sleep time, wake after sleep onset [WASO], sleep latency [time to fall asleep], sleep efficiency [% of time spent in bed sleeping], longest sleep period, night-to-night instability [mean square successive differences])⁴ will be measured using the Actiwatch (Philips Respironics, Bend, OR) for actigraphy. Actigraphy is a valid and reliable measure of sleep that is highly correlated with the clinical gold standard, polysomnography,^{121,122} but more practical for caregivers. The Actiwatch contains a calibrated accelerometer that can interface with a

Table 2. Variables and Measures

VARIABLE	MEASURE	TIME OF MEASURE
Parent Outcomes		Enroll 6 Wk 3M 6M 9M
Psychological Health		
Mental HRQoL	PROMIS [®] (SFv1.2- Global Health)	X X X X X
Depressive Cognitions	Depressive Cognitions Scale	X X X X X
Depressive Symptoms	PROMIS [®] (SFv1.0- Depression 8a)	X X X X X

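### The lead Aim 2 model for hair cortisol pairs 6-week resourcefulness with a 3-month sample, about 46% of whose look-back window precedes the mediator reading

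*Combined protocol and SAP*

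**What the plan says.** The Aim 2 & 4 paragraph of Primary Analyses sets one lead pairing for psychological health, physical health and self-management outcomes, with one mixed model per outcome, described as covering "parent outcomes at 3 months after randomization that adjust for the intervention indicator variable, stratification factors, and the mediator at 6 weeks". The total effect at 3 months is then split into direct and indirect parts, and the proportion mediated is estimated. The same paragraph adds that similar models will use other time points to explore the temporal pattern further. Its example is the effect on "parent outcomes at 6 months that are mediated by personal and/or social resourcefulness at 3 months".

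Hair cortisol (chronic stress) is one of the two physical outcomes in Aim 1, so Aim 2 covers it, and no exception is made for it. Parent Outcome Variables describes a "hair cortisol sample that measures cortisol level over the past 3 months". The study design paragraph gives the schedule: "Chronic stress will be measured by obtaining parents' hair cortisol levels and objective sleep by actigraphy at T1, T3, T4, and T5".

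Baseline cortisol is not named among the covariates of the mediation models. By contrast, Aim 4 names baseline sleep and positive health practices as controls.

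**The concern.** A mediation model needs the outcome to follow the mediator. Measuring resourcefulness at 6 weeks and the outcome at 3 months achieves this for outcomes that describe the parent around the 3-month visit. Even the sleep quality index, which looks back one month, falls after week 6. Hair cortisol looks back over the whole interval from enrollment, so part of the outcome accrues before the mediator is read.

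If lower stress in the first weeks leaves a parent more resourceful at week 6, the lead model will report some of that as mediation through resourcefulness. At stake is the Aim 2 conclusion for chronic stress, since the plan hypothesizes mediation for all study outcomes. The lead model is also the one presented as deciding whether mediation exists. If it and the exploratory 3-month/6-month pairing disagree, nothing in the plan says which governs for cortisol.

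**Working it through.** The plan gives no figure for this point. The first two steps use its own timings; the third rests on stated assumptions.

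**1. Window overlap.** Inputs: look-back of 3 months, about 13 weeks (Parent Outcome Variables); mediator at 6 weeks and outcome at 3 months (Aim 2 & 4). With even accrual:

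share before mediator = (mediator time − window start) / window length

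- 6 weeks → 3 months: (6 − 0)/13 = 46% (6/12 = 50% if 3 months is taken as 12 weeks).
- 3 → 6 months, 6 weeks → 6 months and 6 → 9 months: 0%, because the window opens at or after the mediator reading.

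**2. Arm difference in the clock.** Follow-Up Contacts and Data Collection counts T2 from delivery of the training in the intervention arm and from enrollment in the control arm, while T3 runs from enrollment. No delay between enrollment and training is stated. For assumed delays of 1, 2 or 4 weeks, the intervention-arm share is 7/13 = 54%, 8/13 ≈ 61% or 10/13 = 77%.

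**3. Size of a reverse path when true mediation is zero.** Assumptions, none from the documents:

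- Cortisol in each period has within-arm SD 1, and the intervention lowers it directly by 0.3.
- The intervention raises resourcefulness by 0.5 (residual SD 1).
- Resourcefulness has no effect on cortisol.
- Each SD of week 0–6 cortisol lowers 6-week resourcefulness by r.
- Cortisol in any two periods correlates ρ within a person.

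Arm effect on the mediator: a = 0.5 + 0.3r. Mediator coefficient in the outcome model: b = −r·k/(1 + r²v). Here k is the within-arm covariance of week 0–6 cortisol with the outcome and v is the within-arm variance of week 0–6 cortisol, both conditional on T1 cortisol where adjusted. Then

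false proportion mediated = (0.5 + 0.3r)·r·k / [0.3(1 + r²v)]

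- T3 unadjusted: k = 6/13 + (7/13)ρ, v = 1.
- T4 unadjusted: k = ρ, v = 1.
- T3 adjusted: k = (6/13)(1 − ρ²) + (7/13)(ρ − ρ²), v = 1 − ρ².
- T4 adjusted: k = ρ − ρ², v = 1 − ρ².

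Examples at r = 0.2, ρ = 0.5. T3 unadjusted: 0.56 × 0.2 × 0.731 / (0.3 × 1.04) = 26%. T4 adjusted: 0.56 × 0.2 × 0.25 / (0.3 × 1.03) = 9%.

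| Cortisol sample, with 6-week mediator | ρ | k | v | r = 0.1 | r = 0.2 | r = 0.3 |
|---|---|---|---|---|---|---|
| T3, unadjusted | 0 | 0.46 | 1 | 8% | 17% | 25% |
| T4, unadjusted | 0 | 0 | 1 | 0% | 0% | 0% |
| T3, unadjusted | 0.5 | 0.73 | 1 | 13% | 26% | 40% |
| T3, adjusted for T1 | 0.5 | 0.48 | 0.75 | 8% | 17% | 27% |
| T4, unadjusted | 0.5 | 0.50 | 1 | 9% | 18% | 27% |
| T4, adjusted for T1 | 0.5 | 0.25 | 0.75 | 4–5% | 9% | 14% |

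The first entry of the last row is 4.4% by the formula. Simulation of the same set-up agreed with the ρ = 0.5 rows. Pairing 3-month rather than 6-week resourcefulness with the T4 sample moved the T4 figures by less than one percentage point.

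**The case against.** A reader might infer that mediation of chronic stress cannot be established in this trial at all. The documents do not support that. The Aim 2 & 4 paragraph already plans later pairings and names 3-month resourcefulness with 6-month outcomes, where the windows do not overlap. The gap is confined to the lead cortisol model.

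A reader might also infer that cause and effect are wholly reversed in weeks 0–6. That does not follow either. Under the Resourcefulness Training Intervention arm section and Table 1, skills are taught in one initial session and practised daily for 28 days. Much of the mediator's change may therefore come before its 6-week reading, and some early cortisol may follow that change. Order is blurred, not reversed throughout. For the same reason, a 46% dilution of a true mediated effect would require resourcefulness to act only after week 6.

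It is tempting to treat the 6-month sample as clean. It is so only if a parent's cortisol is uncorrelated across periods. The plan's power calculation assumes exchangeable within-person correlation of outcomes, and its outcome models use random intercepts. With ρ = 0.7 and no baseline adjustment, the formula gives 12%, 25% and 38% at T4 against 15%, 30% and 45% at T3, so changing the time point alone would achieve little.

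The sequential-ignorability analysis in Secondary Analyses has some bearing. A reverse path appears as correlation between the mediator and outcome errors (about −0.06, −0.13 and −0.19 in the ρ = 0 case), and that analysis asks how strong an unobserved confounder would have to be. It can signal fragility, but it neither removes the overlap nor restores the order.

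Finally, the share depends on the window. It would be 19% for a 2-month look-back and 0% for 1 month. The protocol states 3 months.

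**Conclusion.** The point holds for the lead cortisol model only. On the plan's own timings, about 46% of the 3-month hair window precedes the 6-week mediator reading, assuming even accrual over the stated 3 months. The indirect effect and proportion mediated from that model should not be read as mediator-then-outcome evidence. The overlap-free alternative is already in the plan but has the status of exploration.

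The percentages of false mediation are illustrative: they depend on assumed effect sizes and an assumed correlation, and the documents give neither for cortisol. In the scenarios worked, the 6-month sample adjusted for T1 cortisol had less bias than the planned pairing. Where cortisol was correlated across periods, some bias remained, because earlier cortisol can affect both mediator and outcome. The Aim 1 comparison of arms and the mediation models for the other outcomes are not affected.

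**What to change.** In the Aim 2 & 4 paragraph, make three changes for hair cortisol:

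- Name 3-month (or 6-week) resourcefulness with the 6-month sample as the lead mediation model, choosing one before the data are seen.
- Add T1 hair cortisol as a covariate in both the mediator and outcome models.
- Report the 6-week/3-month cortisol pairing as descriptive only.

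Keep the current pairing for the other outcomes. State in the report that the change reduces, but does not remove, bias from earlier cortisol affecting both mediator and outcome.

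The cost is a few sentences. All the measurements are already scheduled. The downside is somewhat more attrition at 6 months than at 3; the plan expects 20–30% by month 9 and gives no figure for month 6.
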